2.5.1.2 MIP and MEP from pulmonary function testing

The change from baseline in MIP % predicted and MEP % predicted will be analyzed separately based on the MMRM model, similar to the primary endpoint described in [Section 2.5.1](#). For each of the endpoints, the model will include the baseline value of the corresponding response variable (either MIP or MEP), age (as continuous variable), gender (male or female), treatment group, visit, and treatment by visit interaction as fixed effects. Due to the correlation between baseline FVC and MIP or MEP, and to avoid potential col-linearity issue, the baseline FVC (used as a randomization stratification factor) is not included in the current MMRM model.

Since the % predicted values can only be calculated for patients with age of 7 or above who have a reference value available, the analyses for MIP % predicted and MEP % predicted will be limited to the mITT patients with age of 8 years or older.

The raw values of MIP and MEP will be summarized descriptively based on mITT.

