11.4.2.1 Analysis of primary efficacy endpoints

Refer to [Section 9.1.1](#) for details on this endpoint.

The primary efficacy endpoint of change from baseline in FVC (% predicted) in upright position to Week 49 will be analyzed in the mITT population using an MMRM with change from baseline as outcome variable. The MMRM model will include the baseline FVC (% predicted) and age (both as continuous variables), gender (male, female), treatment group, visit, and treatment-by-visit interaction as fixed effects. An unstructured covariance matrix shared across treatment groups will be used to model the within-patient error and the Kenward-Roger approximation will be used to estimate the degrees of freedom. The model will be fitted using restricted maximum likelihood. The difference between treatment groups will be estimated based on least-square means at the Week 49 visit within the MMRM model.

The primary analyses will be performed after all mITT patients have been followed for at least 12 months after randomization. This analysis will include all post-baseline assessments up to Week 49, regardless of treatment discontinuation status; missing data will not be imputed and will be assumed to be missing-at-random (MAR).

The primary statistical objective is to test the NI of avalglucosidase alfa versus alglucosidase alfa at 5% level of significance. The null and alternative hypotheses based on an NI margin of 1.1 are described as H_{01} and H_{a1} below:

- H_{01} : avalglucosidase alfa – alglucosidase alfa ≤ -1.1 versus H_{a1} : avalglucosidase alfa – alglucosidase alfa > -1.1

The study will be considered to have met its primary statistical objective if the NI null hypothesis (H_{01}) is rejected, or the lower bound of the 2-sided 95% confidence interval for the least square mean difference of avalglucosidase alfa – alglucosidase alfa is >-1.1 .

After NI is demonstrated, a test for superiority of avalglucosidase alfa versus alglucosidase alfa will be performed with an overall 5% level of significance.

If the superiority null hypothesis of no difference between avalglucosidase alfa and alglucosidase alfa is rejected, and the point estimate for the difference favors avalglucosidase alfa, the statistical superiority of avalglucosidase alfa versus alglucosidase alfa can be claimed.

The same analysis as described above will be performed for the PP population to assess the robustness of the study outcome.

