11.4.2.2 Analyses of secondary efficacy endpoints

Refer to [Section 9.2.1](#) for details on these endpoints.

The secondary efficacy endpoints are change from baseline at week 49 for the following parameters:

- 6MWT distance walked (in meters);
- MIP and MEP% predicted;
- Lower extremity muscle strength (HHD);
- Motor function as assessed by QMFT;
- Health-related quality of life as assessed by SF-12.

Each of the secondary endpoints will be analyzed based on the MMRM model, similar to that described for the primary endpoint (the model will be further adjusted by baseline score of corresponding parameter), using the mITT population (with the exception of SF-12, which will be analyzed for a subset of mITT patients with age ≥ 18). The difference between treatment group will be assessed with least square mean difference at Week 49 estimated within the framework of MMRM model. P-value and corresponding 2-sided 95% CI will be provided.

For 6MWT endpoint, the statistical objective is to demonstrate the superiority of avalglucosidase alfa versus alglucosidase alfa.

For MIP and MEP, the primary analysis will be based on % predicted value in upright position.

For HHD, the primary analysis is based on the lower extremity summary score. For QMFT, the primary analysis is based on the total score, while each individual item score will be summarized descriptively. For SF-12, the PCS and MCS scales will be analyzed separately.

See [Section 11.4.2.3](#) for consideration of multiplicity.

For the Canada-specific requirement regarding HHD refer to Appendix C [Section 17.3.3](#).

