1.1 STUDY DESIGN AND RANDOMIZATION

EFC14028 is a Phase 3, multicenter, multinational, randomized, double-blind study comparing the efficacy and safety of avalglucosidase alfa and alglucosidase alfa (both at 20 mg/kg qow) in treatment-naïve patients with LOPD Ages 3 and above.

Approximately 96 patients will be randomized to receive either avalglucosidase alfa or alglucosidase alfa in a blinded manner. Randomization will be in a 1:1 ratio with stratification factors based on baseline FVC, gender, age (<18 versus ≥ 18), and region (Japan versus Ex-Japan) among patients of age ≥ 18 . Randomization will be performed within each of the following 6 strata:

1. Age <18,
2. Age ≥ 18 , all genders and FVC (% predicted), Japan,
3. Age ≥ 18 , male and FVC (% predicted) <55%, ex-Japan,
4. Age ≥ 18 , female and FVC (% predicted) <55%, ex-Japan,
5. Age ≥ 18 , male and FVC (% predicted) $\geq 55\%$, ex-Japan,
6. Age ≥ 18 , female and FVC (% predicted) $\geq 55\%$, ex-Japan.

The majority of enrolled patients are expected to be ≥ 18 years of age and ex-Japan. For regulatory reasons, patients ≥ 18 years of age from Japan are included as a separate stratum to ensure that at least one such patient is exposed to avalglucosidase alfa. The other strata (age, FVC % predicted, and gender) were chosen to balance the baseline demographics and characteristics of patients thought to influence treatment outcomes in the Phase 3 AGLU02704 (LOTS) study of Myozyme[®]/Lumizyme[®] (alglucosidase alfa). Few patients <18 years of age are expected to be enrolled and so additional strata were not deemed necessary.

If at the end of the recruitment, less than 4 pediatric patients aged 3 to < 18 years are enrolled, up to 2 additional pediatric patients will be enrolled directly in the open-label avalglucosidase alfa long term follow-up phase where they will receive avalglucosidase alfa.

Patients will be observed in a 49 week blinded treatment phase, in which patients will receive an IV infusion of 20 mg/kg avalglucosidase alfa or alglucosidase alfa qow, followed by an open-label treatment extension phase, in which all patients will receive an IV infusion of 20 mg/kg avalglucosidase alfa qow for up to 96 weeks. The 49 week blinded treatment phase will be considered the primary analysis period (PAP).

An extended open-label avalglucosidase alfa long term follow-up period will last up to 144 additional weeks (or up to avalglucosidase alfa approval in the country of the patient,

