2.1.3.1 Primary efficacy endpoint

The primary efficacy endpoint is the change from baseline to Week 49 in FVC (% predicted) in the upright position. FVC will be reported in absolute value in liters, as well as the percent of predicted normal values based on Global Lung Initiative (GLI) 2012 reference equations (3). The FVC percent of predicted values will be calculated based on FVC in liters, gender, race (classified as Caucasian, Asian and African-American, and Other/Mixed), age (at least one decimal place in years), and height (in cm) at the time of each assessment and will be reported centrally from Biomedical Systems (BMS), following pulmonary software specification and user requirement (4).

The FVC percent predicted value is calculated as:

$(\text{actual FVC measurement}/\text{predicted value of FVC}) * 100.$

The GLI-2012 regression equations and lookup tables are used to calculate predicted values of FVC (1). FVC is predicted according to the following equation in the EFC14028 trial:

$M = \exp(a_0 + a_1 \cdot \ln(\text{Height}) + a_2 \cdot \ln(\text{Age}) + a_3 \cdot \text{black} + a_4 \cdot \text{NEAsia} + a_5 \cdot \text{SEAsia} + a_6 \cdot \text{Other} + \text{Mspline})$

where

Black = 1 if a subject is African American, otherwise = 0

NorthEastAsia = 1 if a subject is from North East Asia, otherwise = 0

SouthEastAsia = 1 if a subject is from South East Asia, otherwise = 0

Other = 1 if subject is 'other ethnic group' or mixed ethnicity, otherwise = 0

Coefficients a(n) depend on sex and are given by lookup table

Mspline is age-varying coefficients, given by lookup table for each type of sex

For the analysis purpose, the age will be calculated based on $(\text{assessment date} - \text{birth date} + 1)/365.25$. Height will be based on the most recent valid value at or prior to the assessment date.

Since baseline FVC (% predicted) is used for randomization stratification purposes, no patient should have a missing baseline value. The schedule of assessments is provided in [Section 7](#).

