2.5.1.1 Distance walked in 6MWT

2.5.1.1.1 Primary analysis of 6MWT based on distance walked

The primary statistical objective for 6MWT is to test the superiority of avalglucosidase alfa versus alglucosidase alfa at Week 49 in the mITT.

The change from baseline in total distance walked in 6MWT will be analyzed based on the MMRM model, similar to the primary endpoint described in [Section 2.5.1](#), assuming MAR. The

model will include the total distance walked in 6MWT at baseline, baseline FVC (% predicted) and age (as continuous variables), gender (male or female), treatment group, visit, and treatment-by-visit interaction as fixed effects. The difference between treatment groups will be estimated based on least-square means at the Week 49 visit within the MMRM model. A two-sided 95% confidence interval using the least-square mean difference and its variance will be provided. If the lower bound of the two sided 95% confidence interval for the least square mean difference of avalsuglucosidase alfa–alglucosidase alfa is greater than 0, then the statistical superiority of avalsuglucosidase alfa over alglucosidase alfa is established.

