2.5.1.3 Hand-held dynamometry (lower extremity muscle strength)

Change from baseline in lower extremity muscle strength composite score will be analyzed based on the MMRM model, similar to the primary endpoint described in [Section 2.5.1](#). The model will include summary HHD lower extremity score at baseline, baseline FVC (% predicted) and age (as continuous variables), gender (male or female), treatment group, visit, and treatment-by-visit interaction as fixed effects.

As a supportive analysis, change from baseline in % predicted of the summary score for the lower extremity muscle strength will be analyzed based on the MMRM model, similar to the primary endpoint described in [Section 2.5.1](#). The model will include the % predicted of the summary score at baseline, baseline FVC (% predicted), and age (as continuous variables), gender (male or female), treatment group, visit, baseline HHD % predicted score-by-visit interaction and treatment-by-visit interaction as fixed effects. Similar analyses on the % predicted for each muscle group will be conducted.

Since % predicted values are only available for all muscle groups for patients age 6 or older, the analysis on % predicted HHD lower extremity summary will be performed in mITT patients with an age of 6 or older.

Raw score as well as the % predicted scores for each muscle group will also be summarized descriptively by treatment group and study visit.

In order to evaluate quality of observed changes in muscle strength measured with HHD, a sub-group analysis of HHD data will be performed of data confirmed to be collected by same assessor and with the patient in the same position as baseline and Week 49. HHD outcomes will include all muscle groups and UE and LE composites.

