2.5.1.4 Quick Motor Function Test

Change from baseline in total score of QMFT will be analyzed based on the MMRM model in mITT, similar to the primary endpoint described in [Section 2.5.1](#). The model will include total score at baseline, baseline FVC (% predicted), age (as continuous variables), gender (male or female), treatment group, visit, and treatment-by-visit interaction as fixed effects.

Each individual item of the QMFT will be summarized descriptively.

2.5.1.5 12-item short form health survey

Change from baseline in PCS and MCS will be analyzed separately based on the MMRM model, similar to the primary endpoint described in [Section 2.5.1](#). The model will include baseline score (PCS or MCS), baseline FVC (% predicted), and age (as continuous variables), gender (male or female), treatment group, visit, and treatment-by-visit interaction as fixed effects. Descriptive summary of change over time and shift from baseline will be performed as well.

The analyses will be conducted based on the mITT patients who are of age ≥ 18 at screening/baseline.

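### The confirmatory MIP and MEP models drop baseline FVC to avoid collinearity, which does not materially affect the treatment contrast; the likely cost is a little precision, not bias

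*SAP*

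**What the plan says.** SAP 2.5.1.2 fits MMRMs to change in MIP and MEP (% predicted) with the endpoint's own baseline, age, gender, treatment, visit and treatment-by-visit. It then states that "the baseline FVC (used as a randomization stratification factor) is not included in the current MMRM model". The reason given is that FVC correlates with MIP and MEP and that collinearity might result.

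The SAP's other secondary models do the opposite:

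- 6MWT (2.5.1.1.1): "the total distance walked in 6MWT at baseline, baseline FVC (% predicted) and age (as continuous variables".
- Lower-extremity HHD (2.5.1.3): "summary HHD lower extremity score at baseline, baseline FVC (% predicted) and age (as continuous variables".
- QMFT (2.5.1.4): "The model will include total score at baseline, baseline FVC (% predicted), age (as continuous variables".
- SF-12 (2.5.1.5): baseline PCS or MCS, together with baseline FVC.

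Protocol 11.4.2.2 describes every secondary model as "similar to that described for the primary endpoint (the model will be further adjusted by baseline score of corresponding parameter". Protocol 11.4.2.1 defines that primary model: "The MMRM model will include the baseline FVC (% predicted) and age (both as continuous variables". SAP 1.5 and 1.6, which list statistical changes, do not mention the omission.

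MIP and MEP are the second and third secondary tests in the fixed sequence of SAP 2.5.2, after 6MWT and before HHD.

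**The concern.** SAP 1.1 says that the age, FVC and gender strata were "chosen to balance the baseline demographics and characteristics of patients thought to influence treatment outcomes" in the LOTS study. The MIP and MEP models keep age and gender, so FVC is the only one of the three left out. The stated ground concerns the stability of covariate coefficients, which nobody will interpret here. The quantity that decides the test is the Week 49 treatment difference.

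If FVC predicts change in MIP or MEP beyond the endpoint's own baseline, leaving it out widens the confidence interval. Testing stops at the first non-significant result, so a slightly weaker MIP test also slightly lowers the chance of reaching MEP and HHD.

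**Working it through.** **The plan's nearest figure.** The documents give no SD, effect or power for MIP or MEP. The related figure is the power of the FVC superiority test, which must succeed before any secondary test. Inputs from SAP 1.3: difference 2.0, SD 5.1, 96 patients, 10% missing.

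- Evaluable per arm: 96 × 0.9 / 2 = 43.2, so 43.
- SE = 5.1 × √(2/43) = 1.100; noncentrality = 2.0 / 1.100 = 1.818.
- Two-sided 5% t-test on 84 df: power about 43.5%. SAP Table 4 gives 43.5%, so the figure reproduces.

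**Step 1: what collinearity inflates.** For the endpoint's own baseline, the variance inflation from a correlation r with FVC is 1/(1 − r²). For r = 0.3, 0.5, 0.7 and 0.9 this is 1.10, 1.33, 1.96 and 5.26. For the treatment term, inflation depends on how well the baseline covariates predict the arm, which randomisation keeps near zero. Simulated with stratified blocks, it is about 1.03 at every r from 0.3 to 0.9.

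On the SE scale (single-visit ANCOVA, n = 86, FVC included), the own-baseline SE rises from 0.129 to 0.156 to 0.257 as r goes 0.5, 0.7, 0.9. The treatment SE stays at 0.218. In a four-visit MMRM it stays at 0.2117.

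**Step 2: precision lost by omission.** The unknown input is the share of residual variance that FVC explains beyond own baseline, age and sex (partial R²). All values below are assumed. As a rough guide, the residual SD without FVC is larger by 1/√(1 − partial R²): 1.0%, 2.6% and 5.4% at 2%, 5% and 10%. Omission saves one degree of freedom, which offsets a little of this.

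The MMRM simulation used unstructured covariance, REML, four visits, n = 96, 10 random dropouts, within-patient correlation 0.6 and 400 paired runs per scenario. Change in the Week 49 SE when FVC is omitted:

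| Partial R² | MMRM, r = 0.5 to 0.9 | MMRM, FVC effect growing to Week 49, r = 0.7 | ANCOVA, r = 0.5 to 0.9 |
|---|---|---|---|
| 0% | −0.1 to −0.3% | −0.2% | −0.3 to −0.5% |
| 2% | +0.7 to +0.9% | +0.7% | +0.5 to +0.7% |
| 5% | +2.2 to +2.4% | +2.0% | +2.0 to +2.3% |
| 10% | +4.9 to +5.2% | +4.3% | +4.9 to +5.1% |

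FVC pays for its degree of freedom once it explains about 0.3 to 0.6% of residual variance (MMRM) or 0.7 to 1.1% (ANCOVA).

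**Step 3: power of a hypothetical MIP test.** Suppose the test has 80% power with FVC included. On 80 df that needs a noncentrality of 2.836, which omission divides by the SE ratio. Example at 10%, r = 0.5: 0.2227 / 0.2117 = 1.052; 2.836 / 1.052 = 2.696; power 75.9%. Across the MMRM scenarios, power without FVC is 80.1 to 80.2%, 79.3 to 79.5%, 78.1 to 78.5% and 75.9 to 76.6% at 0%, 2%, 5% and 10%. The largest losses are therefore about 0.7, 1.9 and 4.1 points.

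**Step 4: allowing for the gate.** Multiplying those largest losses by the FVC superiority power, and assuming rough independence: 0.435 × 0.7 = 0.3, 0.435 × 1.9 = 0.8 and 0.435 × 4.1 = 1.8 points. The 6MWT test comes before MIP as well, so the unconditional loss is smaller still.

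**Step 5: bias and type I error.** Estimates were unbiased with and without FVC (mean error at most 0.01 SD). At partial R² 10%, type I error without versus with FVC was 4.43% v 4.84%, 4.28% v 4.83% and 4.72% v 4.97% for r = 0.5, 0.7 and 0.9 (Monte Carlo error about 0.4 points). One exception appeared. With about 10% missing, and missingness depending on FVC in opposite directions in the two arms, omission gave a bias of about −0.04 SD, with rejection still at 5.2%.

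**The case against.** The omission is prespecified, openly stated and given a reason. MIP and MEP come from the same pulmonary function testing as FVC, so their own baselines may already carry most of what FVC would add. The motor and quality-of-life endpoints lack such a respiratory baseline, so different covariate sets are not inconsistent in themselves. This stands: FVC may add little, and if it adds nothing, leaving it out is marginally better. It does not rescue the stated reason, because redundancy is a different argument from collinearity and costs almost nothing to guard against.

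A reader might infer more than the documents support:

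- **A breach of the protocol.** The protocol says only that the secondary models are similar to the primary one. That suggests baseline FVC without requiring it. SAP 1.5 and 1.6 list major or main changes, so their silence shows little.
- **Proof that FVC is prognostic for MIP or MEP.** The remark in SAP 1.1 refers to outcomes in LOTS. It says nothing about MIP or MEP change after adjustment for own baseline.
- **Bias or a raised false-positive rate.** The calculations show neither under randomisation without arm-differential missingness on FVC.
- **A wrong analysis set.** SAP 2.5.1.2 says that % predicted values exist from age 7, yet limits the analysis to age 8 or older. That calls for a clarification, probably affects few or no patients, and adds nothing to this point.

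The sizes are also open to challenge, since every prognostic input is assumed. A second simulation with a stronger assumed FVC effect (0.4 SD per SD, r = 0.3) cut the SE from 0.205 to 0.189 on adding FVC, a fall of 7.8%. The upper end therefore reflects the assumption made.

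**Conclusion.** The point holds as a minor improvement. Avoiding collinearity is not a sound reason to drop baseline FVC from two confirmatory models whose only target is the treatment contrast, and the SAP does not apply that reasoning to its other secondary endpoints.

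The consequence is limited to precision. It ranges from a negligible gain if FVC is not prognostic to a Week 49 SE about 4 to 5% larger if FVC explains 10% of residual variance. The corresponding power losses apply only if the sequence reaches MIP. They rest on assumed partial R², an assumed 80% starting power and random dropout in the MMRM simulation. The documents supply none of these for MIP or MEP.

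**What to change.** Before the primary database lock and unblinding, add baseline FVC (% predicted) as a continuous fixed effect to the MIP and MEP MMRMs, as the SAP already does for 6MWT, HHD, QMFT and SF-12. No new data are needed; SAP 2.1.3.1 notes: "Since baseline FVC (% predicted) is used for randomization stratification purposes, no patient should have a missing baseline value".

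The documents do not state when that lock took place. The SAP was signed in April 2020, and amended protocol 06, dated February 2022, reports the last enrolment in August 2020, so lock has probably passed. In that case the confirmatory model should stay as prespecified, and the FVC-adjusted model should be reported as a labelled sensitivity analysis.

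The cost is one model term and one degree of freedom in each of two analyses. If FVC turns out not to be prognostic, the SE rises by about 0.1 to 0.3% (MMRM) or 0.3 to 0.5% (ANCOVA).

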7.2.1 Exclusion criteria related to study methodology

- E 01. The patient is <3 years of age.
- E 02. The patient has known Pompe specific cardiac hypertrophy.
- E 03. The patient is wheelchair dependent.
- E 04. The patient is not able to ambulate 40 meters (approximately 130 feet) without stopping and without an assistive device. Use of assistive device for community ambulation is appropriate.
- E 05. The patient requires invasive-ventilation (non-invasive ventilation is allowed).
- E 06. The patient is not able to successfully perform repeated FVC measurements in upright position of $\geq 30\%$ predicted and $\leq 85\%$ predicted.
- E 07. The patient has had previous treatment with alglucosidase alfa or any investigational therapy for Pompe disease.
- E 08. The patient (and patient's legal guardian if patient is legally minor as defined by local regulation) is (are) not able to comply with the clinical protocol.
- E 09. The patient is concurrently participating in another clinical study using investigational treatment or has taken other investigational drugs or prohibited concomitant medications within 30 days or 5 half-lives from screening or randomization, whichever is longer.

- E 10. The patient has known history of drug or alcohol abuse within 6 months prior to the time of screening.
- E 11. The patient has clinically significant organic disease (with the exception of symptoms relating to Pompe disease), including clinically significant cardiovascular, hepatobiliary, pulmonary, neurologic, or renal disease, or other medical condition, serious intercurrent illness, or extenuating circumstance that, in the opinion of the Investigator, precludes participation in the study or potentially decreases survival.
- E 12. Patient with prior or current use of immune tolerance induction therapy.

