Pulmonary function testing

Secondary efficacy endpoints measured by pulmonary function tests (PFT) will include the assessment of MEP and MIP in the upright position. Additional parameters of respiratory function, including assessment of FVC, MIP, and MEP in the supine position. FEV₁, and PEF in the upright and supine positions will be considered exploratory or tertiary endpoints.

All PFTs will be reported centrally from BMS following pulmonary software specification and user requirement (4).

The percent predicted values for MIP and MEP will be calculated (9, 10). The normal reference values used for % predicted calculation will be dependent on each patient’s age, gender, and weight (Table 6). For each patient, the same equations used for the baseline will be used to calculate the predicted values (eg, if a patient started at ≤17 years of age and turns 18 during the study, he/she will still use the pediatric formula after turning to 18). For analysis purposes, the age will be calculated based on (assessment date - birth date + 1)/365.25. Weight for age <18 will be based on the most recent valid value at or prior to the assessment date. The percent (%) predicted value is defined as (absolute measurement/normal reference value) * 100.

Since the reference values will be available only for patients of age 7 years or older, the % predicted MIP and MEP will not be derived for patients aged <7.

Table 6 - Reference equations for predicted value of MEP and MIP

Test/Age at baseline	Male	Female
MEP		
≥18 years old (9)	$174 - 0.83 * \text{age}$	$131 - 0.86 * \text{age}$
7–17 years old (10)	$35 + 5.5 * \text{age}$	$24 + 4.8 * \text{age}$
MIP		
≥18 years old (9)	$120 - 0.41 * \text{age}$	$108 - 0.61 * \text{age}$
7–17 years old (10)	$44.5 + 0.75 * \text{weight}$	$40 + 0.57 * \text{weight}$

Age in years; weight in kg.

Hand-held dynamometry (lower extremity muscle strength)

Equipment for hand-held dynamometry (11) using the make technique will be standardized across sites. During the treatment period, the assessment will be completed before the IMP infusion. Stabilization procedures for all muscles groups will be followed to avoid use of compensatory muscles. To complete a make test, the examiner holds the dynamometer stationary while the patient exerts a maximal force against the dynamometer. The patient makes a gradual increase in force and then completes an isometric hold for 4-5 seconds.

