2.5.2 Multiplicity issues

A sequential test strategy for the primary efficacy endpoint and key secondary endpoints will be used to control Type 1 error rate at 5% in a strong sense. Testing will proceed according to the following order and will stop if there is a non-significant comparison:

1. The primary efficacy endpoint of FVC (% predicted) will be tested for NI of avalglucosidase alfa versus alglucosidase alfa first.
2. If NI is demonstrated, the superiority of the avalglucosidase alfa versus alglucosidase alfa in FVC (% predicted) will be tested with the same overall 5% significance level.
3. If the superiority of avalglucosidase alfa versus alglucosidase alfa is demonstrated on the primary efficacy endpoint, the hypothesis testing for the secondary efficacy endpoints will proceed according to the following order:
 - a) Change from baseline to Week 49 in total distance walked in 6MWT (a superiority test with a two-sided alpha of 0.05),

- b) Change from baseline to Week 49 in % predicted of MIP (a superiority test with a two-sided alpha of 0.05),
- c) Change from baseline to Week 49 in % predicted of MEP (a superiority test with a two-sided alpha of 0.05),
- d) Change from baseline to Week 49 in summary score of lower extremity strength by HHD (a superiority test with a two-sided alpha of 0.05).

Analyses of additional secondary endpoints will be considered for supportive purposes.

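### The confirmatory MIP and MEP analyses start at age 8, although the SAP derives % predicted values from age 7 and gives no reason for the gap

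*SAP*

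**What the plan says.** SAP 2.1.3.2, under pulmonary function testing, explains that "the reference values will be available only for patients of age 7 years or older" and draws the consequence that "the % predicted MIP and MEP will not be derived for patients aged <7". Table 6 in that section has two age bands, classified by age at baseline: 18 and over, and 7 to 17.

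SAP 2.5.1.2 sets the analysis population. It gives the reason first, "Since the % predicted values can only be calculated for patients with age of 7 or above who have a reference value available", and then concludes that the analyses "will be limited to the mITT patients with age of 8 years or older". Raw MIP and MEP are to be summarised descriptively in the mITT population.

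Protocol 11.4.2.2 analyses each secondary endpoint in the mITT population, "with the exception of SF-12, which will be analyzed for a subset of mITT patients" aged 18 or over. It names no age limit for MIP or MEP.

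SAP 2.5.2 places % predicted MIP at step 3b and % predicted MEP at step 3c of the fixed sequence, each a superiority test at two-sided 0.05. Protocol 11.4.2.3 has the same order.

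**The concern.** The reason and the rule do not match. If the only obstacle is the lack of a reference value below age 7, the limit that follows is 7. A limit of 8 removes a further year of age in which the SAP's own equations produce an endpoint.

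Children of that age can be randomised: the only age exclusion, in Protocol 7.2.1, is "The patient is <3 years of age". As written, the rule would discard valid mITT data from two tests in the sequence that protects the type I error rate. The analysis population for such tests should be correct and unambiguous before treatment codes are released.

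**Working it through.** **Which ages have an endpoint, and which are analysed**

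| Age at baseline | Equation in SAP Table 6 | % predicted derived (SAP 2.1.3.2) | Analysed (SAP 2.5.1.2) |
|---|---|---|---|
| 3 to 6 | none | no | no |
| 7 | paediatric, 7 to 17 | yes | **no** |
| 8 to 17 | paediatric, 7 to 17 | yes | yes |
| 18 and over | adult | yes | yes |

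The two rules differ in one row. As an example from Table 6, predicted MEP at age 7 is 35 + 5.5 × 7 = 73.5 for a boy and 24 + 4.8 × 7 = 57.6 for a girl. Predicted MIP at that age depends only on weight (44.5 + 0.75 × weight for boys, 40 + 0.57 × weight for girls). Nothing is missing for a 7-year-old.

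**Is there a reason for 8 elsewhere?**

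- SAP 2.5.1.3 has the parallel rule for dynamometry. Reference values for all muscle groups start at age 6, and the % predicted analysis is done from age 6. There the two limits agree.
- SAP 2.5.1 uses age 8 for an FDA-specific exploratory analysis that matches the lower age limit of LOTS. It applies the primary FVC method and does not mention MIP or MEP. SAP 2.5.1.2 cites reference values, not LOTS.
- SAP 1.5 and 1.6 list the statistical changes. An age limit for MIP and MEP is not among them.

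**How many patients**

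SAP 1.1 expects few patients under 18. Protocol 6.1 allows children to enter the open-label phase directly only if fewer than 4 are enrolled by the end of recruitment. The rationale for amended protocol 06 reports that a child was enrolled that way in August 2020. By inference, at most 3 randomised patients were under 18. The affected number is therefore 0 to 3, and 3 would require every randomised child to be exactly 7. An estimate of 0 to 1 is reasonable.

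**What that costs in precision**

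The documents give no power for MIP or MEP, so there is no stated figure to correct. To set a scale, take the evaluable number behind SAP Table 4: 96 × 0.90 = 86.4, so 86, or 43 per arm. That reproduces the plan's FVC figure. With difference 2.0, margin 1.1 and SD 5.1, the standard error is 5.1 × √(2/43) = 1.10, the noncentrality is 3.1/1.10 = 2.82 on 84 degrees of freedom, and two-sample t-test power is 79.6%, as in Table 4.

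Now assume, for illustration only, that the MIP or MEP test has 80% power at 43 per arm. The standard error grows by the factor √[(1/n₁ + 1/n₂)/(2/43)].

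| Patients lost | n₁, n₂ | SE factor | Power |
|---|---|---|---|
| 0 | 43, 43 | 1.000 | 80.0% |
| 1 | 42, 43 | 1.006 | 79.5% |
| 2 | 42, 42 | 1.012 | about 79.1% |
| 3 | 41, 42 or 40, 43 | 1.018 to 1.019 | 78.5% to 78.6% |

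**Which age counts**

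SAP 2.5.1.2 does not say whether age is taken at baseline or at assessment. Table 6 classifies by age at baseline, while SAP 2.1.3.2 computes age from the assessment date for the equations. Week 49 is Day 337 (SAP Table 14), which is 336 days after Day 1, and 336/365.25 = 0.92 of a year. If birthdays are spread evenly, about 92% of children aged 7 at baseline would be 8 by then. Under an age-at-assessment reading such a child would be in the analysis at Week 49 but could be out at earlier visits.

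**The case against.** The strongest reply is that this is a one-year slip with almost no practical effect. The documents do not show that any 7-year-old was randomised, and children enrolled directly into the open-label phase are outside the randomised population. Read as age at baseline, the cut is a pre-randomisation characteristic applied alike to both arms, so it favours neither. The testing order and alpha are untouched, and raw values are still described for everyone in the mITT population. All of that stands.

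A second point is that a limit of 7 also falls short of the full mITT population in the protocol. That is true, but excluding children under 7 is unavoidable because they have no reference value. Excluding those aged 7 is a choice.

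A third is that 8 may have been intended, since it is the LOTS lower age limit. The SAP does not say so for these endpoints, and the reason it does give points to 7, as does the dynamometry rule. The possibility can be met by letting the sponsor justify 8 explicitly.

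Finally, whether a 7-year-old is dropped altogether depends on the age reference, which the section leaves open. This limits the claim to the age-at-baseline reading and is a second reason to amend the sentence.

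**Conclusion.** The concern holds. SAP 2.5.1.2 sets the population for two confirmatory tests one year above the age at which the SAP's own equations begin, and the reason it offers supports 7. A 7-year-old with valid MIP and MEP data would be excluded, on the reading that age is taken at baseline, as in Table 6.

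The size is small: probably 0 to 1 patient of about 96, and at most 3 by inference from the open-label enrolment rule. Under the illustrative 80% power assumption, the loss is at most about 1.5 percentage points. No figure stated in the documents changes, and neither bias nor type I error is at issue. The case for correction rests on a clear population rule for tests in the hierarchy, not on a likely change in the result.

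**What to change.** In SAP 2.5.1.2, replace the limit of 8 with 7 years or older at baseline. The analysed set is then every mITT patient whose age permits a % predicted value, and the age reference agrees with Table 6. If 8 was intended, state the reason in SAP 2.5.1.2 and list it in SAP 1.6 as a departure from the mITT population in Protocol 11.4.2.2.

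The cost is one number and two words, with no statistical penalty if done before unblinding. SAP 1.1 releases the randomisation list only after final SAP approval and database lock. If the codes have already been released, record the change as a clarification and report how many patients it affects.
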